4.9.4. Presentation of Concentration Data

4.9.4.1. Handling of Missing Data

Missing concentration data will be considered as non-informative and will not be imputed. No concentration estimates will be provided for missing sample values.

4.9.4.2. Listing and Presentation of Individual PK Data

- The sampling time of pre-dose samples relative to dosing is treated as zero for all sampling periods separately
- All concentrations are presented in original units as reported by the Bioanalytical laboratory
- All concentrations that are below the limit of quantification (BLQ) are set to zero
- Listings of PK sampling times include nominal and actual time elapsed from dose with the deviation from the nominal time and measured concentrations of the drug
- No further imputation will be applied to any missing values

Individual IXT-m200 concentration data will be listed by subject, visit, timepoint, and treatment group.

An overlay plot (Spaghetti plot) of subjects by treatment group will be presented graphically on both linear and semi-logarithmic scales for IXT-m200.

4.9.4.3. Summary of PK Concentration

For PK concentration summaries, the following applies:

- All concentrations that are BLQ are set to zero
- The sampling time of pre-dose samples relative to dosing will be treated as zero
- Drug concentrations will be summarized by nominal time point
- Descriptive statistics will be performed
- No further imputation is applied to any missing values
- IXT-m200 concentrations will be summarized by treatment group, visit, and time point.
- Mean (±SD) serum concentration versus time will be presented graphically on both linear and semi-logarithmic scales by treatment for IXT-m200.

4.9.5. PK Parameters Derivation

For the derivation of PK parameters, the following rules will apply:

- All concentration values below the assay's lower limit of quantification (BLQ) will be treated as zero
- The sampling time of pre-dose samples relative to dosing will also be treated as zero
- Actual blood sampling times will be used to derive PK parameters (if the actual blood sampling is not present, then that timepoint and concentration will not be considered for PK analyses (except for predose, where timepoint as zero will be considered))
- No further imputation will be applied to any missing values

Individual IXT-m200 PK parameters will be listed by subject, visit, and treatment group.

Additionally, box plots of PK exposure parameters (e.g., AUC, C_{max}) and HACA results may be presented, as appropriate.

4.9.5.1. PK Parameters Summarization

PK parameters and concentrations data will be summarized using the following descriptive statistics:

Variable	Summarized with:				
PK concentration at each nominal time point	n, number and percentage of subjects with BLQ, arithmetic mean, SD, coefficient of variance (CV) %, minimum, median, maximum, geometric mean and geometric CV%				
$\begin{array}{c} AUC_{0\text{-t}},AUC_{0\text{-28d}},\\ AUC_{0\text{-inf}},AUC_{0\text{-tau}},C_{max},\\ C_{max,ss},CL,CL_{ss},V\text{ and }\\ V_{ss} \end{array}$	n, arithmetic mean, SD, CV%, minimum, median, maximum, geometric mean and geometric CV%				
t _{1/2} , k _{el} and ratios (RC _{max} and RAUC)	n, arithmetic mean, SD, CV%, minimum, median, maximum				
T _{max} and T _{max,ss} (actual time)	n, minimum, median, and maximum				

Note: CV% = SD/mean in %. n = non-missing No. of observations.

4.9.5.2. PK Reporting Precision

The following precision will be applied to the various descriptive statistics:

Variables	Precision				
Minimum; Maximum	3 significant digits / as needed based on actual measured				
	values				
Arithmetic mean;	4 significant digits / as needed based on actual measured				
Geometric mean; Median	values				
SD	5 significant digits / as needed based on actual measured				
	values				
CV%; Geometric CV%	1 decimal place / as needed based on actual measured				
	values				

For PK concentration and parameter listings, the final reportable results or data will be presented by rounding off to 2 decimal digits, except for the following situations (this applies to individual data):

- Kel data, and Rsq adjusted: rounded off to four decimal digits.
- PK parameters related to time such as T_{max}. T_{max,ss}, K_{el Lower}, and K_{el Upper} must be reported with the same precision as the actual sampling time: rounded off to 3 decimal digits.
- Concentration versus time data: reported as they appear in the corresponding dataset.

4.10. Safety Analyses

Primary analyses of safety will be summarized for the Safety population.

4.10.1. Adverse Events

All adverse events (AEs) will be coded using MedDRA terms. The number and percent of participants with any treatment-emergent AE will be presented by MedDRA SOC and PT in descending frequency of occurrence. If a participant reports more than one AE that was coded to the same SOC or PT, the participant will be counted only once for that specific SOC or PT.

Summaries of AEs by MedDRA SOC and PT will be provided for the following:

- AEs (overall and by severity)
- AEs reported as potentially related to IXT-m200 (including those with missing
- relatedness designation) (overall and by severity)
- Serious adverse events (SAEs)
- AEs leading to study withdrawal
- AEs leading to treatment discontinuation

Summaries will be presented by treatment group and for all participants. A listing will include all events for each participant, along with study day of onset, duration, severity, seriousness, relatedness, action taken (e.g., treatment discontinued, study discontinued, treatment interrupted, none), and outcome (e.g., recovered/resolved, recovering/resolving, recovered/resolved with sequelae, not recovered/not resolved, fatal, unknown). Separate participant listings of SAEs and AEs leading to withdrawal will also be presented.

If any participant dies during the study, a listing of the fatal AE will also be provided along with a participant narrative that will include all relevant information.

4.10.2. Clinical Laboratory Analyses

All quantitative centrally reviewed clinical laboratory results other than urinalysis results will be presented in standardized units. Both observed values and changes from baseline will be summarized for each scheduled timepoint. Figures will be used if appropriate and would include shading between the lower and upper limits of normal, as applicable.

4.10.3. Electrocardiograms

Electrocardiogram (ECG) measurement data will be summarized descriptively by timepoint. Both observed values and changes from baseline will be summarized for each scheduled timepoint, as well as depicted in figures. Abnormal values will be indicated in listings.

4.10.4. Vital Signs

Vital signs results (heart rate, diastolic and systolic blood pressure, temperature, and respiratory rate) will be summarized descriptively by treatment and planned timepoint. Both observed values and changes from baseline will be summarized for each scheduled timepoint and depicted in figures.

4.10.5. Physical Examination

Physical examination findings will be listed by treatment group, participant, and visit.

4.10.6. Psychiatric evaluation

Psychiatric evaluation findings will be listed by treatment group, participant, and visit.

4.11. Immunogenicity

The primary analysis of immunogenicity will be conducted using the ITT population. Secondary analyses of immunogenicity will be conducted using the mITT population. The secondary endpoint of the number and percentage of participants with anti-IXT-m200 antibody levels that are confirmed positive and have titers more than three times the minimum required dilution will be summarized by treatment group and overall. For participants with positive screen results whose samples underwent immunodepletion, the number and percentage of participants with each titer category will be presented.

4.12. Subgroup analyses

Primary and secondary efficacy analyses may be performed in the following subgroups:

- Sex: male versus female
- Gender (as collected on eCRF)
- BMI categorized as under/normal/overweight
- Abstinent during the grace period: abstinent versus not abstinent
- Baseline METH use as randomized: <18 days versus >18 days
- Treatment compliance: above versus below median doses of study drug received
- Preferred route of administration of methamphetamine
- CBT attendance compliance: above versus below median number of sessions attended
- Participants who received additional therapy outside of the study versus those who did not
- If at least 10% participants are in the ITT population but not the PP population, the PP population will be analyzed as a subgroup.

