1.2. Study Design

InterveXion's protocol M200C-2201 is a Phase 2, double-blind, placebo-controlled, multiple-dose study of the safety and efficacy of monthly intravenous (IV) doses of IXT-m200 in treatment-seeking individuals with METH use disorder. The study was stopped before enrolling Cohort 2. As such, any reference to Cohort 2 in this document no longer applies, but has been retained for reference.

The study consists of two cohorts:

- In Cohort 1, approximately 60 participants will be randomized in a 2:1 ratio to IXT-m200 1.5 g or placebo (saline).
- In Cohort 2, approximately 60 participants will be randomized in a 2:1 ratio to the recommended dose of IXT-m200 or placebo based on the interim analysis at the end of Cohort 1. If the interim analysis recommends maintaining a dose of 1.5 g, then the sample size will be recalculated.

In each cohort, participants will receive either study drug (IXT-m200 at the cohort-specific dose or placebo) at the beginning of Weeks 1, 5, 9, 13, 17, and 21. All participants will also participate in seven sessions of a standardized cognitive behavioral therapy (CBT) program which will be delivered by a trained therapist; the first dose of IXT-m200 or placebo is intended to be given on the same day of initiation of CBT. For Cohort 1, the participants will participate in the CBT sessions during their monthly visits. For Cohort 2, participants will go to the clinic weekly for saliva drug tests and will participate in CBT sessions every two weeks, starting with Week 1. Participants will be followed at monthly intervals through Week 33. Cohort 1 will use app-based assessments to monitor between visits and Cohort 2 will use TLFB to monitor between visits. Schema 1.2 in the protocol displays the schematic of the study design for Cohort 1, and Appendix 1 shows the schedule of events. The first four weeks of treatment will be considered a grace period, designed to accommodate the likelihood that participants will relapse initially and experience the effects of IXT-m200. It further allows participants time to absorb and incorporate some of the skills taught by cognitive behavior therapy. METH use endpoints will be analyzed in the weeks following the grace period.

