4.1.5. Definition of Study Time Points

Baseline is the latest pre-dose assessment with a non-missing value on or before the date of randomization (Day 1). If time is not collected, Day 1 assessments are assumed to be taken prior to first dose and used as baseline. If baseline data are missing, no derivation will be performed, and baseline will be set to missing.

The following conversion factors will be used to convert days to weeks, months, and years: 1 week = 7 days, 1 month = 30.4375 days, and 1 year = 365.25 days.

For all randomized participants, Day 1 is the date of randomization. Day 1 is the planned timepoint for the first dose administration. Day 1 is also the start of "Week 1".

For assessments on or after the randomization date, time is calculated in days as:

Study Day = Assessment Date - Randomization Date + 1 (positive number)

For assessments prior to the randomization date, time is calculated in days as:

Study Day = Assessment Date – Randomization Date

For other time variables based on two dates, Duration (days) = End Date - Start Date + 1.

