4.5.3. Concomitant Medications

All concomitant medications (i.e., prescription medications, over-the-counter medications, non-prescription medications, and supplements) taken during study participation will be recorded on the eCRF. For this protocol, a prescription medication is defined as a medication that can be prescribed only by a properly authorized/licensed clinician.

The use of concomitant medications will be summarized by therapeutic class and generic medication name using descriptive statistics. Concomitant medications will include all medications taken from randomization through follow-up.

In addition, any behavioral therapy sessions with a trained provider outside the protocol will be recorded as concomitant therapy.

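### SAP 4.12 allows efficacy comparisons in four subgroups formed after randomisation, where bias is possible, and its two median cuts leave participants at the median unassigned

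*SAP*

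**What the plan says.** SAP section 4.12 opens with "Primary and secondary efficacy analyses may be performed in the following subgroups". Four of the listed groups depend on what happens during the trial:

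- The first is early use status: "Abstinent during the grace period: abstinent versus not abstinent".
- The second is based on dosing: "Treatment compliance: above versus below median doses of study drug received".
- The third splits attendance at CBT in the same way, at the median session count.
- The fourth, which concerns care from elsewhere, reads "Participants who received additional therapy outside of the study versus those who did not".

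Other sections fix the timing. SAP 4.1.5: "For all randomized participants, Day 1 is the date of randomization". SAP 1.2: "The first four weeks of treatment will be considered a grace period". SAP 4.5.3: "any behavioral therapy sessions with a trained provider outside the protocol will be recorded as concomitant therapy".

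Protocol section 9.4.7 lists the first three, with both median cuts in the same form. Outside therapy appears only in the SAP. The last entry in both lists treats the per-protocol (PP) population as a subgroup if at least 10% of participants fall outside it.

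Neither document says what to do with participants at the median or whether the median is pooled or taken by arm. SAP 4.5.2 gives no numerical compliance threshold. Neither subgroup section labels any of these comparisons as non-randomised.

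**The concern.** Randomisation makes the arms comparable at Day 1. If a subgroup is defined by something treatment can change, those who enter it on active drug may differ from those who enter it on placebo, and the arm difference inside it mixes drug effect with selection. Results of this kind are easily summarised as the drug working in compliers or in early abstainers. SAP 2.2 says the trial is meant to supply information for planning Phase 3, so such a reading from about 60 participants could mislead.

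The median cuts add a definitional problem. Doses and CBT sessions are small counts with a ceiling, so many participants can share the median value, and read literally the cut puts them in neither group.

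**Working it through.** **The plan's own figure.** The plan gives no figure for these subgroups. Its nearest number, the detectable difference in SAP Table 4 for 40 versus 20 at 80% power (0.78 SD), reproduces as 0.780 SD from a noncentral t with 58 degrees of freedom and noncentrality d × √(40×20/60). It is not in dispute.

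**Step 1: can treatment affect the grouping variable?**

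| Group | When known | Route from treatment |
|---|---|---|
| Grace-period abstinence | After the first four weeks on drug | SAP 1.2 expects participants to experience the drug's effects in this window |
| Doses received | Up to Week 21 | Protocol 6.1.2 ends dosing after an SAE attributed to study drug; protocol 7.2 allows discontinuation for AEs or on request |
| CBT sessions | Up to Week 29 | Six of the seven sessions fall on dosing visits (schedule of events), so this largely repeats the dose variable |
| Outside therapy | During participation | Relapse could prompt it |

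The PP set depends on protocol deviations and on treatment received (SAP section 3), so it too is formed after randomisation.

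**Step 2: overlap of the dose subgroup with the endpoint.** The primary endpoint covers the 20 weeks after the Week 5 visit (protocol 9.4.2), and SAP 4.6.1 scores every week after withdrawal as not abstinent. Take a participant who misses no dose and withdraws just after the k-th dosing visit (k from 2 to 6). The highest possible score is 4(k − 2)/20:

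- k = 3 (Week 9): 3 doses, at most 4/20 = 20%
- k = 5 (Week 17): 5 doses, at most 12/20 = 60%
- k = 6 (Week 21): 6 doses, at most 16/20 = 80%

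For those who withdraw, a low dose count imposes a low score.

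**Step 3: when is the high-dose group empty?** Inputs: at most 6 doses (protocol 6.1.2); about 60 participants, because Cohort 2 was not enrolled (SAP 1.2). The ITT set includes randomised participants who were never dosed, so the count runs from 0 to 6. The pooled median of 60 values is the mean of the 30th and 31st ordered values. It equals 6 exactly when at least 31 participants receive all six doses, and then nobody lies above it.

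| Receive all 6 | Literal cut: above / below | Unassigned | At or above / below |
|---|---|---|---|
| 31 | 0 / 29 | 31 | 31 / 29 |
| 36 | 0 / 24 | 36 | 36 / 24 |
| 42 | 0 / 18 | 42 | 42 / 18 |
| 48 | 0 / 12 | 48 | 48 / 12 |

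**Step 4: how likely is that?** The documents give no dose-completion rate, so c, the chance of receiving all six doses, is an assumption. P(empty) = P(X ≥ 31) with X ~ Binomial(60, c):

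- c = 0.40: 4%
- c = 0.50: 45%
- c = 0.60: 93%
- c = 0.70: 99.9%

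Intermittent missed visits lower c. With retention r to the last dose and an independent chance m of missing each of doses 2 to 6, c = r(1 − m)^5:

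- r = 0.70, m = 0.05: c = 0.70 × 0.774 = 0.542, P(empty) about 70%
- r = 0.70, m = 0.10: c = 0.70 × 0.590 = 0.413, about 7%
- r = 0.50, m = 0.05: c = 0.50 × 0.774 = 0.387, about 3%
- r = 0.50, m = 0.10: c = 0.50 × 0.590 = 0.295, under 0.1%

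For seven CBT sessions the exponent is 6. At r = 0.70 and m = 0.05, c = 0.70 × 0.735 = 0.515 and P(empty) is about 54%.

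Ties remain when the high group is not empty. In simulations with constant dropout, the average number at the median dose count, over all simulated trials, was 9 to 10 of 60 at 50% retention with 5% or 10% missed visits, and 27 and 17 of 60 at 70% retention.

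**The case against.** The strongest reply is that little depends on these analyses. They are optional, the p-values are nominal (SAP 4.1.1), the SAP calls the study exploratory (SAP 2.2 and 2.3), and SAP 4.6.1 ties a showing of efficacy to the primary ANCOVA alone. All of that stands and limits the severity.

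The second reply is that an empty high group would be noticed at once and that assigning ties to the upper group would cure it. That is true of ties, but the cure leaves a subgroup formed after randomisation.

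Three stronger readings are tempting and not supported:

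- **That these comparisons are biased by a known amount or in a known direction.** The documents give no data on how treatment changes compliance, early abstinence or outside therapy. They support only that the comparisons can be biased.
- **That the high-compliance group will be empty.** The plan cites dropout of up to 50% (SAP 2.2), and protocol 7.2 lets participants miss doses and return. Under several plausible combinations the chance is small.
- **That the trial's main efficacy result is compromised.** The primary analysis uses all randomised participants and none of these groups.

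**Conclusion.** The point holds as a low-severity improvement. Four optional efficacy subgroups, and the conditional PP subgroup, are formed after randomisation without being labelled so. Bias within them is possible, with size and direction unknown. The dose subgroup is in addition partly determined by the outcome, through the scoring of weeks after withdrawal.

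The tie problem is certain in wording and conditional in effect. Anyone at the median is unassigned, and the high-dose group disappears if 31 or more of 60 receive all six doses. The chance of that runs from about 4% to 99.9% as the assumed all-six-dose rate goes from 0.40 to 0.70. It rests on a pooled median, N = 60, independence between participants and, where missed visits are included, an assumed miss rate. The tie rule alone would be a small omission; the post-randomisation grouping is the main reason to amend.

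**What to change.** In SAP 4.12:

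1. Limit treatment-effect subgroup analyses to baseline factors: sex, gender, BMI, METH-use stratum and route of administration.
2. Present grace-period abstinence, doses received, CBT attendance and outside therapy as descriptive tables by arm, labelled non-randomised and without treatment-effect p-values.
3. Replace the median cuts with fixed categories that place everyone: all 6 doses versus fewer, and all 7 CBT sessions versus fewer. These are reporting categories only; they settle ties and do not make the groups randomised.
4. Describe the PP analysis as a non-randomised sensitivity analysis, not a subgroup.
5. Correct SAP 4.13, which reports no changes from the protocol although the outside-therapy subgroup is absent from protocol 9.4.7.

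The cost is a wording change with no new data. What is given up is the nominal p-values for these optional subgroups; the descriptive information is kept.

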4.13. Changes to Protocol-Planned Analyses

• There are no changes to the analyses planned in the protocol.

5. Supporting Documentation

5.1. Appendix 1: Schedule of Events

Assessment a	Screening	Dosing (-2/+7 days)				Follow-up (±3 days)			ET		
Study Week	≤-1	1	5	9	13	17	21	25	29	33	NA
Study Day	-60 to -1	1 ^b	29	57	85	113	141	169	197	225	NA
Informed consent	X										
Initial evaluations											
Eligibility criteria											
Demographics											
Medical history and medications	X										
Vital signs ^c	Α										
Physical and psychiatric exam											
Urine pregnancy test											
Saliva drug screen											
Laboratory tests d	X	X	X	X	X	X	X	X			X
Electrocardiogram (ECG) e	X	X	X	X	X	X	X				
App training											
App download and tutorial	X										
Saliva drug screens until acceptable											
Quality of Life Assessments f	X				X			X		X	X
Methamphetamine Use Assessments	X							X		X	X
Randomization		X									
Blood for PK/HACA & Cytokines g		X	X	X	X	X	X	X	X	X	X
Dose administration h		X	X	X	X	X	X				
Cognitive behavioral therapy		X	X	X	X	X	X		X		
Wellness check											
Update medical history											
Update medications											
Brief psychiatric evaluation		X	X	X	X	X	X	X	X	X	X
Vital signs ^c											
Targeted physical exam											
Urine pregnancy test											
Continuous events											
AE monitoring i											
Recovery coaching j						Con	tinuous				
Self-report daily drug use by app											
Random saliva drug screens k	14.64 1		1		11 >			1.1 DI		1.	

Abbreviations: ET - early termination; HACA - human anti-chimeric antibodies; NA - not applicable; PK - pharmacokinetic

^a Descriptions of assessments are in Section 8.1 (efficacy) or 8.2 (safety).

^b Study Day -1 is the day prior to the first dose. Study Day 1 is the day of the first dose.

^c Vital sign measurements will be taken on dosing days starting with a pre-dose measurement (≤30 min prior), then 0.25, 0.5, 1, 2, and 4 hours (±5 min) after dosing starts, and as needed afterward until normalization. Measurements will be obtained once on each non-dosing day. Each test may be repeated once at each time point if the initial result is out of range.

^d Laboratory tests require blood and urine sampling for hematology, serum chemistry, and urinalysis. Samples are to be taken 2-hr post-dose completion (±10 min) on dose days.

^e ECGs are to be done 30-min post dose completion (±15 min) on dosing days.

f Quality of Life Assessments include TEA, PGIC, and CGIC.

